1.1 Study Design

This is a single-arm Simon two-stage phase 2 clinical trial to evaluate the dual antithrombotic and antineoplastic activity of zafirlukast in tumor marker-only relapsed ovarian cancer.

1.1 Primary Objective

The primary objective is to determine efficacy of zafirlukast in terms of CA-125 response rate per Gynecologic Cancer Intergroup (GCIG) criteria.

1.2 Key Secondary Objective

Assess changes in CA-125 doubling time in the 3 months prior to enrollment and following initiation of zafirlukast

1.3 Exploratory Objectives

- Measure changes PDI and ERp57 inhibitory activity in plasma
- Measure changes in platelet-dependent thrombin generation
- Determine progression free survival (PFS)
- Assess the incidence of venous thromboembolism
- Assess incidence of major hemorrhage and clinically relevant non-major bleeding

2. BACKGROUND

2.1 Study Disease(s)

Ovarian Cancer

Epithelial ovarian cancer is the seventh most common malignancy among women with 230,000 women diagnosed annually. The rate of survival is poor, with an approximately 50% survival at 5 years following diagnosis [1]. Debulking surgery is considered front-line treatment for women with ovarian cancer with neoadjuvant and/or adjuvant chemotherapy administered for more advanced disease. Intravenous administration of carboplatin and paclitaxel is the standard first-line chemotherapy for advanced ovarian cancer. Two randomized trials demonstrated improved progression free survival with the addition of maintenance bevacizumab in high-risk stage III disease without improved overall survival [2, 3], although more recent work has called these findings into question [4]. More recently, poly ADP ribose polymerase (PARP) inhibitors have shown improved progression free survival as maintenance therapy in the first line setting for all patients, though patients with BRCA-mutated ovarian cancer gained the most benefit[5, 6]. PARP inhibitors are approved for all patients after platinum-based chemotherapy with a platinum sensitive relapse [7-9], and those patients with BRCA-mutated ovarian cancer have improved overall survival with this approach[10],

Version Date: 12/21/22

Monitoring for recurrence of ovarian cancer following initial therapy includes serial measurement of the tumor marker CA-125. Tumor marker-only relapse is defined as the absence of recurrent disease by imaging or symptoms along with a rising CA-125, i.e. CA-125 more than twice the upper limit of normal (35 U/mL) in the setting of a normal baseline CA-125 levels or CA-125 greater than twice the nadir count on two successive measurements for CA-125 values that remain above baseline. A randomized study evaluated the benefit of early versus delayed chemotherapy in patients with tumor marker-only relapse of ovarian cancer [11]. Early treatment was started within 28 days of CA-125 increase while delayed treatment was started in response to clinical or symptomatic relapse. There was no difference in overall survival between the arms. In light of these results, observation is currently standard-of-care for tumor marker-only relapsed ovarian cancer. For patients desiring systemic treatment, endocrine therapy is typically preferred given reduced toxicity compared to cytotoxic chemotherapy. This approach has been observed to result in a 17% response rate in CA-125 per GCIG criteria in patients with estrogen receptor-positive ovarian cancer [12]. However, it has not been shown to improve progression-free or overall survival compared to observation in this population.

Venous Thromboembolism and Ovarian Cancer

Venous thromboembolism (VTE) is commonly observed in cancer patients. It is a leading cause of morbidity and is associated with increased mortality in this population [13, 14]. In high-risk cancer patients especially where protocol-driven radiographic monitoring for deep vein thrombosis is implemented, the incidence of VTE within the initial few months of chemotherapy often exceeds 15% [15-17]. Ovarian cancer is among the most prothrombotic malignancies. According to Medicare discharge data, ovarian cancer was associated with the highest incidence of cancer-associated VTE [18]. Similarly, in large registries from California (528,693 adults) and the Netherlands (66,329 adults), the incidence of VTE in ovarian cancer patients exceeded essentially that of all other malignancies including pancreatic cancer and malignant glioma [19, 20]. Patients with advanced malignancies are also at an increased risk of bleeding [21]. Notably, apixaban, a direct oral anticoagulant, was recently shown to be efficacious in reducing VTE in cancer patients but were also associated with a doubling in rate of major hemorrhage [22]. Developing antithrombotics that reduce the incidence of VTE without increasing the risk of major hemorrhage would broadly impact the care of patients with advanced malignancy.

Protein Disulfide Isomerase

PDI is a member of a large family of thiol isomerase/disulfide oxidoreductases exist in humans [23]. These thiol isomerases are generally capable of oxidation reduction and isomerization reactions. Recent studies have determined that a subset of thiol isomerases, including PDI, ERp5, ERp57, and ERp72 have extracellular activity, which play important roles in both arterial and venous thrombosis as well as in a variety of cancers. PDI, ERp5, ERp57, and ERp72 are secreted

by platelets and reattach to the plasma membrane, where they function as extracellular oxidoreductases [24-27]. They are required for thrombus formation and fibrin formation [26, 28-31], as well as for platelet aggregation, dense granule secretion, fibrinogen binding, and calcium mobilization [25].

Thiol isomerases are also upregulated in many distinct cancer types, including ovarian, prostate, lung, melanoma, lymphoma, and glioma, while inhibition of PDI is cytotoxic in ovarian cancer and multiple myeloma cell lines [29, 32]. Increased levels of thiol isomerases have been positively correlated increased oncogenic transformation [33], gene transcription [34], metastasis [35], and even promoting resistance to chemotherapy [36] and radiation [37]. Similar to its role in platelets, thiol isomerases can also be secreted from tumor cells and perform functions on the cell surface [38].

In the context of thromboembolic disease, PDI is released from activated platelets and endothelial cells and is thought to modulate through oxidation, reduction, or isomerization a number of extracellular substrates, the best characterized being vitronectin [29, 39-43]. Targeting PDI activity with blocking antibodies or small molecules prevents both platelet accumulation and fibrin generation at the site of vascular injury in several distinct animal models of thrombosis [28, 30, 39, 44, 45].

Several small molecule inhibitors of PDI have been identified. In pharmacokinetic/pharmacodynamics study conducted in healthy volunteers, isoquercetin inhibited PDI activity in plasma and reduced platelet-dependent thrombin generation in a dose and timedependent manner [41]. In a recently completed a phase II clinical trial in advanced cancer patients demonstrating that daily isoquercetin significantly reduced coagulation markers of the thrombosis (i.e. D-Dimer and thrombin generation) and prevented the development of VTE (Figure 1). Isoquercetin was well tolerated without any attributable significant adverse events reported and no major hemorrhages observed [46].

[figure not shown]

Figure 1. The PDI inhibitor, isoquercetin, reduces the hypercoagulability of advanced malignancy. Patients with advanced lung, colorectal, and pancreatic cancer were treated with isoquercetin 1000 mg daily for 2 months. Shown in figure are the waterfall plots for comparison with baseline measurements. A) D-dimer plasma concentrations decreased by a median of 20% equating to a median decrease of 206 ng/ml fibrinogen equivalent units (P<0.001). B) Median decrease of circulating soluble P-selectin was 58% (P<0.001) and C) platelet-dependent thrombin generation decreased by 55% (P=0.006).

Zafirlukast was recently identified through a small molecule screen as an inhibitor of PDI along with other thiol isomerases including ERp5, ERp57, ERp72. Similar to isoquercetin, zafirlukast reduces platelet aggregation and fibrin generation in a dose-dependent manner as shown in Figure 2.

[figure not shown]

Figure 2 – (A) Washed human platelets were incubated with ZFL or vehicle for 5 minutes prior to stimulation with collagen for 180 seconds in an optical aggregometer. (B) Data were normalized to vehicle and % inhibition of aggregation (mean + SEM) calculated, n=12. (C) Fibrinogen binding was measured by flow cytometry. Platelets were incubated with vehicle or ZFL (0.6- 20μ M) for 5 minutes prior to stimulation with 0.25 μ g/mL CRP-XL n=6. Graphs represent mean \pm SEM. Data was analyzed by one-way ANOVA *p<0.05, **p<0.01, ***p<0.005.

The expression of PDI and other thiol isomerases are increased in ovarian cancer and increased PDI expression has been associated with disease progression and shortened survival [47]. Small molecule inhibitors of PDI such as propynoic acid carbomyl methyl amides (PACMA) have been shown to reduce tumor growth in human ovarian cancer mouse xenografts [48]. Zafirlukast inhibits ovarian cancer cell growth as shown in Figure 3 in a dose-dependent manner.

[figure not shown]

Figure 3 – The effect of Zafirlukast on cancer cell viability was determined by the Prestoblue assay. Cells were seeded at 3,000 cells/well in a 96 well plate and drug treated 24 hours later. After a 24 hour incubation, cell viability was determined per the manufacturer's instructions.

Updated results of trial in women with tumor-marker only relapsed ovarian cancer:

We enrolled a total of four women who received zafirlukast 40 mg twice daily and performed serial CA-125 measurements to assess for tumor response. None of the women demonstrated a decrease in CA-125 following the initiation of zafirlukast. However, in all 4 women the rate of rise of CA-125 was reduced following treatment with zafirulast (Figure 4). Accordingly, the mean change in CA-125 was 0.036 U/mL per day prior to treatment compared with 0.015 U/mL per day following zafirlukast (paired t-test p=0.026). This equated to a mean CA-125 doubling time of 29.8 days in the weeks prior to treatment compared with a mean doubling time of 85.69 days following treatment. There were no grade 3 or higher toxicities observed on study. As shown in Figure 4B, there was only modest inhibition of PDI activity in plasma as measured by Di-eosin-

GSSG assay. In the study subject who demonstrated the greatest PDI inhibition there was the CA-125 doubling was most pronounced. These data suggest that higher doses of zafirlukast may provide additional PDI inhibitory activity and further inhibit ovarian cancer cell growth.

[figure not shown]

Figure 4. CA-125 doubling time following zafirlukast in women with ovarian cancer. A) Comparison of CA-125 doubling time before and after start of zafirlukast. B) Inhibition of plasma PDI activity before and 28 days following initiation of zafirlukast.

2.2 IND Agent

2.2.1 Zafirlukast

Zafirlukast (Accolate) is FDA approved for the treatment of asthma in children and adults. Its effectiveness in asthma is attributed to its activity as a competitive receptor antagonist to leukotriene D4 and E4[49].

Zafirlukast is rapidly absorbed following oral administration and 99% is bound to plasma protein in circulation. Zafirlukast is extensively metabolized in the liver. Hydroxylated metabolites are excreted in the feces and formed through cytochrome P450 2C9 pathway. In patients with biopsy-proven cirrhosis, the clearance of zafirlukast is 50-60% slower compared to healthy subjects. There is no apparent effect on pharmacokinetic profile in renal insufficiency.

While the FDA approved dose of zafirlukast is 20 mg twice daily, doses up to 80 mg twice daily appear well tolerated. In a randomized clinical study with over 360 patients to assess asthma response, observed side effects were similar in cohort receiving zafirlukast 80 mg twice daily compared to placebo for 6 weeks [50]. Serious adverse events were reported in two patients receiving zafirlukast (e.g. detached retina and exacerbation of asthma). Two patients developed transient increase in liver transaminases which resolved in one patient despite continuing therapy and another after withdrawal of treatment.

Following oral ingestion of zafirlukast 40 mg the peak plasma concentration is \sim 3 μ M which approximates the IC50 for both inhibition of cell viability, *ex vivo* platelet inhibition and PDI inhibitory activity [51].

2.3 Rationale

Version Date: 12/21/22

The rationale to evaluate zafirluast as a dual phase 2 study in this population are several-fold. First, zafirlukast and other PDI inhibitors have demonstrated anti-tumor activity in preclinical ovarian cancer models [48]. PDI and ERp57 are both upregulated in ovarian cancer and correlate with tumor progression [47]. Women with ovarian cancer following surgery and adjuvant chemotherapy often relapse with tumor marker only (i.e. elevation of CA-125) in the absence of measurable disease by radiographic imaging. Patients are typically monitored without therapy in this setting and are a stated unmet need for a chemotherapeutic with favorable toxicity profile [52]. Finally, ovarian cancer is one of the most prothrombotic malignancies [19] and PDI inhibition has been shown to reduce the hypercoagulability associated with advanced cancer.

3. PARTICIPANT SELECTION

Laboratory tests required for eligibility must be completed within 14 days prior to the date of registration. Baseline measurements must be documented from tests within 14 days of the date of registration for protocols requiring measurable disease. Diagnostic tests, such as CT scans, must be performed within 4 weeks of the date of registration.

3.1 Eligibility Criteria

- 3.1.1 Participants must have histologically confirmed epithelial ovarian, fallopian tube, or primary peritoneal cancer.
- 3.1.2 Participants must have completed at least first-line platinum based chemotherapy and surgery with a response, in the opinion of the investigator, defined as no evidence of disease progression or rising CA-125 at any time during front-line treatment.
- 3.1.3 Participants must meet criteria for tumor marker-only relapse, defined as CA-125 more than twice the upper limit of normal (35 U/mL) in the setting of a normal baseline CA-125 levels or CA-125 greater than twice the nadir count on two successive measurements for CA-125 values that remain above baseline without measurable radiographic disease.
- 3.1.4 Minimum age ≥ 18 years. Because no dosing or adverse event data are currently available on the use of zafirlukast in participants under 18 years of age with ovarian cancer, children are excluded from this study but will be eligible for future pediatric trials.
- 3.1.5 Life expectancy of greater than 4 months.
- 3.1.6 ECOG performance status ≤ 2 (Karnofsky $\geq 60\%$, see Appendix A).
- 3.1.7 Participants must be able to swallow tablets.
- 3.1.8 Participants must have adequate organ and marrow function as defined below:
 - Absolute neutrophil count ≥1,000/mcL

Version Date: 12/21/22

- Platelets >90.000/mcL

- Total bilirubin $\leq 1.3 \times \text{institutional upper limit of normal (ULN)}$

AST(SGOT)/ALT(SGPT)
 Creatinine
 ≤ 2 × institutional ULN
 ≤ institutional ULN

OR

- Glomerular filtration rate (GFR) \geq 45 mL/min/1.73 m²

- 3.1.9 The effects of zafirlukast on the developing human fetus are incompletely characterized. For this reason, women of child-bearing potential must agree to use adequate contraception (hormonal or barrier method of birth control; abstinence) prior to study entry and for the duration of study participation. Should a woman become pregnant or suspect she is pregnant while she or her partner is participating in this study, she should inform her treating physician immediately. Men are not eligible for this study.
- 3.1.10 Ability to understand and the willingness to sign a written informed consent document.

3.2 Exclusion Criteria

Participants who exhibit any of the following conditions at screening will not be eligible for admission into the study.

- 3.2.1 Non-epithelial tumors (pure sarcomas) or ovarian tumors with low malignant potential (ie borderline tumors) or mucinous tumors. Mixed mullerian tumors or carcinosarcomas are allowed.
- 3.2.2 Participants who have had cytotoxic chemotherapy including bevacizumab or radiotherapy within 4 weeks prior to entering the study. This does not include maintenance therapy with a PARP inhibitor, such as olaparib or niraparib. (PARP inhibitor, rucaparib is not allowed to be co-administed with CYP2C9 substrates as maintenance therapy as it could increase exposure to zafirlukast).
- 3.2.3 Participants who have ongoing adverse effects from prior anti-cancer therapy greater than National Cancer Institute (NCI) Common Terminology Criteria for Adverse Events (CTCAE, v5.0) Grade 1, with the exception of Grade 2 non-hematologic toxicity such as alopecia and peripheral neuropathy.
- 3.2.4 Participants who are receiving any other investigational agents.
- 3.2.5 Participants with known brain metastases should be excluded from this clinical trial because of their poor prognosis and because they often develop progressive neurologic dysfunction that would confound the evaluation of neurologic and other adverse events.
- 3.2.6 History of allergic reactions attributed to compounds of similar chemical or biologic composition to zafirlukast.

Version Date: 12/21/22

- 3.2.7 Currently receiving anticoagulant therapy.
- 3.2.8 Current daily use of aspirin (> 81 mg daily), clopidogrel (Plavix), cilostazol (Pletal), aspirin-dipyridamole (Aggrenox) (within 10 days) or considered to use regular use of higher doses of non-steroidal anti-inflammatory agents as determined by the treating physician (e.g. ibuprofen > 800 mg daily or equivalent).
- 3.2.9 Participants receiving any medications or substances that are inhibitors or inducers of CYP2C9 are ineligible. Because the lists of these agents are constantly changing, it is important to regularly consult a frequently updated medical reference. As part of the enrollment/informed consent procedures, the participant will be counseled on the risk of interactions with other agents, and what to do if new medications need to be prescribed or if the participant is considering a new over-the-counter medicine or herbal product.
- 3.2.10 Participants with uncontrolled intercurrent illness.
- 3.2.11 Participants with psychiatric illness/social situations that would limit compliance with study requirements.
- 3.2.12 Pregnant women are excluded from this study because zafirlukast is a class B agent with the potential for teratogenic or abortifacient effects. Because there is an unknown but potential risk for adverse events in nursing infants secondary to treatment of the mother with zafirlukast, breastfeeding should be discontinued if the mother is treated with zafirlukast.

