1.3 Agent Administration

Zafirlukast will be supplied as oral tablets.

Cohort 1: Two tablets (total of 40 mg) will be consumed twice daily. Cohort 2: Four tablets (total of 80 mg) will be consumed twice daily.

Dose modifications will not be made. Tablets will be dispensed from the research pharmacy on day 1 of each cycle. The tablets will be packaged as a 30-day supply (to allow for unexpected occurrences such as dropped tablet).

Tablets should be taken without food. Food decreases the bioavailability of zafirlukast by 40%. Therefore, participants will be instructed to take zafirlukast on an empty stomach, 1 hour before and 2 hours after meals. Missed doses must be taken within four hours of scheduled dose. If longer than four hours, or if dose vomited, skip dose. Subjects will keep a drug diary that will be provided to them by the study team. Subjects will be instructed to return any unused drug. The unused returns will be counted by pharmacy and destroyed on-site per policy.

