1.5 Criteria for Taking a Participant Off Protocol Therapy

Duration of therapy will be ongoing (+/- 7 days inclusion of windows) for up to 12 cycles or until one of the following criteria apply:

- Intercurrent illness that prevents further administration of treatment
- Unacceptable adverse event(s)
- Participant demonstrates an inability or unwillingness to comply with the oral medication regimen and/or documentation requirements
- Participant decides to withdraw from the study, or general or specific changes in the
 participant's condition render the participant unacceptable for further treatment in the
 opinion of the treating investigator
- Clinical or radiographic progression of ovarian cancer
- Doubling the pre-treatment CA-125 value (confirmed at least 1 week apart)
- Grade 3 or 4 hemorrhage and/or symptomatic bleeding in a critical area or organ such as intracranial, intraspinal, intraocular, retroperitoneal, intra-articular or pericardial, or intramuscular with compartment syndrome, and/or bleeding causing a fall in hemoglobin level > 2 g/dL or bleeding leading to a transfusion of > 2 units of packed red blood cells

Version Date: 12/21/22

Participants will be removed from the protocol therapy when any of the criteria listed above applies. The reason for removal from protocol therapy, and the date the participant was removed, must be documented in the study-specific case report form (CRF). Alternative care options will be discussed with the participant.

In the event of unusual or life-threatening complications, participating investigators must immediately notify the Principal Investigator, [name] at [contact].

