2. DOSING DELAYS/DOSE MODIFICATIONS

Dose delays will be made as indicated in the following table(s). The descriptions and grading scales found in the revised NCI Common Terminology Criteria for Adverse Events (CTCAE) version 5.0 will be utilized for dose delays and dose modifications. A copy of the CTCAE version 5.0can be downloaded from the CTEP website

 $\underline{http://ctep.cancer.gov/protocolDevelopment/electronic_applications/ctc.htm}.$

Thrombocytopenia	Management/Next Dose for Zafirlukast
≤ Grade 1	No change in dose
Grade 2	No change in dose
Grade 3	Hold until \leq Grade 1. Resume at same dose level.
Grade 4	Do not restart

Version Date: 12/21/22

ALT/AST	Management/Next Dose for Zafirlukast
≤ Grade 1	No change in dose
Grade 2	Hold until within normal range. Resume at same dose level.
Grade 3	Do not restart
Grade 4	Do not restart

Bilirubin	Management/Next Dose for Zafirlukast
≤ Grade 1	No change in dose
Grade 2	Hold until within normal range. Resume at same dose level.
Grade 3	Do not restart.
Grade 4	Do not restart

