4.1 Zafirlukast

4.1.1 Description

Zafirlukast is a synthetic, selective peptide leukotriene receptor antagonist (LTRA), with the chemical name 4-(5-cyclopentyloxycarbonylamino-1-methyl-indol-3-ylmethyl)-3-methoxy-N-o-tolylsulfonylbenzamide.

Zafirlukast is rapidly absorbed following oral administration. Peak plasma concentrations are generally achieved 3 hours after oral administration. The absolute bioavailability of zafirlukast is unknown. In two separate studies, one using a high fat and the other a high protein meal, administration of zafirlukast with food reduced the mean bioavailability by approximately 40%.

Zafirlukast is more than 99% bound to plasma proteins, predominantly albumin. The degree of binding was independent of concentration in the clinically relevant range. The apparent steady-state volume of distribution is approximately 70 L, suggesting moderate distribution into tissues. Studies in rats using radiolabeled zafirlukast indicate minimal distribution across the blood-brain barrier.

Zafirlukast is extensively metabolized. The most common metabolic products are hydroxylated metabolites which are excreted in the feces. The metabolites of zafirlukast identified in plasma are at least 90 times less potent as LTD4 receptor antagonists than zafirlukast in a standard in vitro test of activity. In vitro studies using human liver microsomes showed that the hydroxylated metabolites of zafirlukast excreted in the feces are formed through the cytochrome P450 2C9 (CYP2C9) pathway. Additional in vitro studies utilizing human liver microsomes show that zafirlukast inhibits the cytochrome P450 CYP3A4 and CYP2C9 isoenzymes at concentrations close to the clinically achieved total plasma concentrations.

Version Date: 12/21/22

The apparent oral clearance (CL/f) of zafirlukast is approximately 20 L/h. Studies in the rat and dog suggest that biliary excretion is the primary route of excretion. Following oral administration of radiolabeled zafirlukast to volunteers, urinary excretion accounts for approximately 10% of the dose and the remainder is excreted in feces. Zafirlukast is not detected in urine.

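### Known cirrhosis is not an exclusion, although the protocol reports 50-60% slower zafirlukast clearance in cirrhosis and cohort 2 takes 80 mg twice daily

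*Combined protocol and SAP*

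**What the plan says.** The protocol treats altered zafirlukast exposure as a reason not to enrol a woman when a drug is the cause. Criterion 3.2.9 reads "Participants receiving any medications or substances that are inhibitors or inducers of CYP2C9 are ineligible". Criterion 3.2.2 does not allow rucaparib maintenance "as it could increase exposure to zafirlukast". Section 4.1.1 (Description) identifies CYP2C9 as the pathway that forms the hydroxylated metabolites.

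Section 2.2.1 attaches a figure for reduced clearance to one patient condition: "In patients with biopsy-proven cirrhosis, the clearance of zafirlukast is 50-60% slower compared to healthy subjects". Neither 3.1 nor 3.2 names cirrhosis or any other chronic liver disease. The entry criteria that bear on the liver are the 3.1.8 limits: total bilirubin up to 1.3 x ULN, AST/ALT up to 2 x ULN and, indirectly, platelets above 90,000/mcL. Criterion 3.2.10 covers intercurrent illness only if it is uncontrolled.

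Cohort 2 takes 80 mg twice daily. On tolerability, section 2.2.1 says that "doses up to 80 mg twice daily appear well tolerated", citing a 6-week asthma study. Under Agent Administration, "Dose modifications will not be made". Treatment continues "for up to 12 cycles or until one of the following criteria apply". The Dosing Delays section says, for grade 2 AST/ALT or bilirubin, "Hold until within normal range. Resume at same dose level"; at grade 3 or 4 the drug is not restarted.

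**The concern.** The plan excludes drugs that could alter exposure and gives no size for any of those interactions. It leaves open the one patient condition for which it does give a size. A woman with stable, known cirrhosis and near-normal liver tests meets every listed criterion, and confirming eligibility against that list would not stop her.

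The issue is patient safety, mainly in cohort 2. Section 3.1.1 (Adverse Event List) says that liver enzyme elevations in controlled trials were rare and mostly seen at four times the recommended dose. With a recommended dose of 20 mg twice daily, that is 4 x 20 = 80 mg twice daily, the cohort 2 dose. The same section says that post-marketing hepatic events occurred mainly in females, with rare cases of liver failure, transplantation and death. This trial enrols only women. The documents describe no experience above that exposure, so a woman who clears the drug slowly would be outside it.

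There is a smaller cost to interpretation. Cohort 2 has four women and is meant to show PDI inhibition and CA-125 doubling time at 80 mg. One woman with about twice the intended exposure would be a quarter of the cohort.

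**Working it through.** The plan states no exposure multiple, so there is no figure of its own to reproduce. The check derives one from the protocol's inputs.

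**Inputs**
- Normal clearance, section 4.1.1: "The apparent oral clearance (CL/f) of zafirlukast is approximately 20 L/h".
- Effect of cirrhosis, section 2.2.1: 50-60% slower.
- Doses, Treatment Regimen and Agent Administration: 40 mg twice daily (cohort 1) and 80 mg twice daily (cohort 2).
- Kinetics, section 4.1.1: approximately linear from 5 mg to 80 mg.
- Duration: at most 12 cycles of 28 days, against 6 weeks in the cited asthma study.

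**Formula.** At steady state, exposure per dosing interval = dose / (CL/f). At a fixed dose, the exposure ratio is normal clearance divided by reduced clearance, so the 20 L/h cancels.

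**Reference exposure** (80 mg, normal clearance): 80 / 20 = 4.0 mg·h/L.

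**Literal reading** (clearance falls by 50-60%):
- 50%: CL/f = 20 x 0.50 = 10 L/h; 80 / 10 = 8.0 mg·h/L; 8.0 / 4.0 = 2.0 times.
- 60%: CL/f = 20 x 0.40 = 8 L/h; 80 / 8 = 10.0 mg·h/L; 10.0 / 4.0 = 2.5 times.

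**Weaker reading** (exposure rises by 50-60%):
- CL/f = 20 / 1.5 = 13.3 L/h; exposure 6.0 mg·h/L; 1.5 times.
- CL/f = 20 / 1.6 = 12.5 L/h; exposure 6.4 mg·h/L; 1.6 times.

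**The same woman at 40 mg**, against the 80 mg reference of 4.0:
- Lowest, weaker reading: 40 / 13.3 = 3.0 mg·h/L, or 0.75 times.
- Highest, literal reading: 40 / 8 = 5.0 mg·h/L, or 1.25 times.

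At 40 mg she is therefore near or below the highest exposure described as tolerated, apart from the upper end of the literal reading. At 80 mg she is above it on either reading. Tolerability in the first four women, at 40 mg, does not settle the question for cohort 2.

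**Duration ceiling.** 12 x 28 = 336 days = 48 weeks; 48 / 6 = 8 times the length of the asthma study.

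**Entry and on-treatment safeguards.** The calendar's chemistry panel consists of total bilirubin, BUN, creatinine, AST and ALT; it lists no albumin or clotting test. Chemistry is drawn on cycle 1 days 1, 8, 15 and 22, on cycle 2 days 1 and 15, and then on day 1 of each later cycle. The hold and stop rules act on those results, so they act only after exposure has begun.

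**The case against.** The strongest reply is that the link between the cirrhosis figure and an eligible woman is not in the documents. Section 2.2.1 gives no severity or laboratory values for its patients. A woman with well-compensated disease who passes 3.1.8 might clear the drug normally. This stands: the multiple is conditional, and the full range for such a woman is 1.0 to 2.5.

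Second, the protocol screens on liver function rather than on diagnosis, which is a legitimate choice. A drug interaction needs its own rule because liver tests at entry cannot detect it. Criterion 3.2.9 also bars inducers, so high exposure is not its only concern. These points weaken the argument from inconsistency. They do not show that the 3.1.8 limits identify slow clearance in known cirrhosis, and rucaparib is barred expressly because of higher exposure.

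Third, 48 weeks is a ceiling. Treatment stops at progression or at a confirmed doubling of pre-treatment CA-125. The mean doubling time at 40 mg was 85.69 days. If doubling were similar at 80 mg, that is 85.69 / 7 = 12.2 weeks, about twice the 6-week study rather than eight times. This stands as a caution on the duration figure; the exposure ratio is unaffected.

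Fourth, chemistry is most frequent in the first two cycles, a grade 2 event requires return to the normal range before restart, and grade 3 or 4 ends treatment. These rules lower the risk materially. After a grade 2 event, however, the drug is resumed at the dose that preceded it, and no reduction is possible.

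Last, cohort 2 has four women, and the investigator taking the history will know of a known diagnosis. Both points are fair, but nothing in the criteria tells the investigator to act on it.

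**Conclusion.** The concern holds. The protocol reports a clearance reduction in cirrhosis large enough to matter at the cohort 2 dose, and no criterion keeps a woman with known cirrhosis out. If the reported figure applies to her, 80 mg twice daily gives her 2.0 to 2.5 times the highest exposure described as tolerated on the literal reading, or 1.5 to 1.6 times on the weaker one.

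This rests on four assumptions: the figure carries over to a woman within 3.1.8 (if not, the factor may be as low as 1.0); the absorbed fraction is unchanged; clearance stays constant at concentrations above those that 80 mg produces with normal clearance; and 80 mg with normal clearance is the right reference. The dose itself stays within the 5-80 mg range described as linear.

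The number of women affected is not given and is probably very small. The change should be made because the possible harm is serious and the correction is nearly free. Confidence is medium, since the documents do not show raised exposure in a woman who would actually qualify.

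**What to change.** Add one exclusion to 3.2, beside 3.2.9: *known cirrhosis, as established from the baseline medical history*. Whether to extend it to other chronic liver disease is for the sponsor's medical lead, because the documents give no exposure figure for that group. No dose rule or additional test is proposed.

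The cost is one eligibility line and one checklist item, using a history already taken at baseline. The loss of eligible women should be negligible. With the exclusion in place, a woman with diagnosed cirrhosis no longer enters, and those enrolled with normal clearance stay at about 1.0 times the reference exposure at 80 mg. The criterion will not catch undiagnosed cirrhosis; there the 3.1.8 limits and the hold and stop rules remain the safeguard.
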